3.1.1. Baseline Definition

In general, the baseline value for efficacy variables and for safety variables is the value associated with the last available pre first dose visit/time point at which the variable was to be collected according to the schedule of study procedures, and must have been collected pre-dose.

3.1.2. Study Day

If the date of interest occurs on or after the first dose/randomization date, then study day will be calculated as (date of interest – date of first dose) + 1.

If the date of interest occurs prior to the first dose/randomization date, then study day will be calculated as (date of interest – date of first dose).

3.1.3. Visit Windows

The visit indicated on the CRF will be used in summaries of the data.

3.1.4. Multiple Assessments

In general, if multiple, valid, non-missing observations exist at a visit or collection time point then records will be chosen based on the following:

- The record closest to the nominal time point in question.

If 2 records are equidistant:

- The later record of the two visits.

If 2 records with same date/time

- Average (generally applies to assessments done in triplicate).

There is a special rule for laboratory test results: if there are multiple valid records within the visit window for the same visit or time point, the record(s) with the latest collection time will be selected rather than the record(s) with collection time closest to the nominal time. The protocol states that:

Additional and repeat laboratory safety testing for the evaluation of abnormal results and/or adverse events during the Study may be performed at the discretion of the investigator or upon request of the Sponsor.

Hence, the latest laboratory test result associated with a visit or time point will be selected for summarization. All results will be provided in listings.

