## 7.2. Clinical Laboratory Abnormalities and Other Abnormal Assessments as Adverse Events or Serious Adverse Events

Abnormal laboratory findings (such as clinical chemistry, hematology, or urinalysis) or other abnormal assessments (such as electrocardiograms [ECGs], X-rays, or vital signs) that are associated with signs and/or symptoms or are considered clinically significant in the judgment of the investigator must be recorded as AEs or SAEs if they meet the definition of an adverse event (or serious adverse event), as described in Section 7.1.1 (Adverse Event) and Section 7.1.2 (Serious Adverse Event).

Clinical laboratory abnormalities of concern may include, but are not limited to, the following where the investigator must recheck within 2-7 days, except for AST or ALT > 3x ULN where these need to be rechecked within 48-72 hours, as deemed appropriate by the investigator:

- clinically significant reduction in neutrophils or leukocytes or lymphocytes that may place subjects at higher risk for infection such as:
  - moderate or severe neutropenia (e.g., absolute neutrophil count of < 1.0 x 10^9/L)
  - moderate or severe leukopenia (e.g., white blood cell count of < 2.0 x 10^9/L)
  - moderate or severe lymphocytopenia (e.g., absolute lymphocyte count of < 0.5 x 10^9/L)
- abnormal hepatic panel (AST or ALT > 3x ULN)
- an excessive decrease in creatinine clearance [e.g., a reduction by ≥ 50% from baseline (baseline for this purpose is defined as creatinine clearance calculated for Day 1, predose activities)]

Depending on the subject's baseline and individual scenario, the investigator should report as an AESI and stop study drug treatment if any of the below is seen:

- moderate or severe neutropenia (e.g., absolute neutrophil count of < 1.0 x 10^9/L) on two sequential laboratory reports
- moderate or severe leukopenia (e.g., white blood cell count of < 2.0 x 10^9/L) on two sequential laboratory reports
- moderate or severe lymphocytopenia (e.g., absolute lymphocyte count of < 0.5 x 10^9/L) on two sequential laboratory reports
- a reduction by ≥ 50% from baseline in creatinine clearance on two sequential laboratory reports
- ALT or AST > 8x ULN on a single laboratory report. Note: See [Appendix 6](#) for an algorithm of evaluating and managing subjects with ALT or AST > 3x ULN.

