### **8.6.3. Laboratory Data**

Safety laboratory values and C-reactive protein values, changes from baseline, values relative to normal ranges, and clinical laboratory abnormalities of concern will be summarized by visit, overall and by arm. C-reactive protein, [REDACTED] total cholesterol, LDL, HDL, and triglycerides levels will be log-transformed for summarization.

Reference ranges provided by the laboratory for each test will be used to evaluate the clinical significance of laboratory test results. Values falling outside the relevant reference range will be flagged, as appropriate, in the data listings. Clinical laboratory abnormalities of concern will be listed in a separate listing. A listing of pregnancy test results will be provided.

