1. INTRODUCTION

This statistical analysis plan (SAP) outlines the planned summarization and analysis of clinical data collected in the long-term safety (LTS) study of Protocol 0164 for TD-1473. Specifications for tables, figures, and data listings are contained in a separate document.

The results of the planned analyses will be presented in a synoptic clinical study report (CSR) which will include analyses of study subject data and safety endpoints. Inferential statistical tests will not be performed. The protocol-planned efficacy analyses will be excluded as they are not necessary for a synoptic CSR.

The 0164 study was terminated early due to lack of efficacy in the 0157 study, for all subjects the date of last dose occurred by 09SEP2021 and the end of study visit by 11OCT2021.

The analysis of pharmacokinetics data (derivation and summarization of individual PK parameters) is outside the scope of this document and is not addressed here.

This document describes the a priori plan for analysis. Any substantive modification to this analysis plan will be identified in the CSR.

Information in the appendices to the SAP are not considered a formal section of the signed SAP.

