1.4. Schedule of Assessments

Table 4: Schedule of Study Procedures

Study Procedures	Day 1	WEEK VISITS +/- 5 Days								Early Study Drug Discontinuation ^l + 5 days from last dose	EOS 4 Weeks Post Last Dose ^l - 3 to + 5 days
		Year 1	W4	W12		W24	W36	W48	W52		
		Year 2			W60	W72	W84	W96	W104		
		Year 3			W108	W120	W132	W144	W156		
Informed Consent	X										
Review Inclusion/Exclusion Criteria	X										
Physician Global Assessment (PGA)	X		X	X	X	X	X	X	X	X	X
Pregnancy Test (females of child-bearing potential)	X		X ^e	X ^e	X ^e	X ^e	X ^e	X ^e	X ^e	X ^e	X ^e
FSH	X ^a										
████████████████████	■			■		■		■		■	■
In Clinic Dosing - Study Drug Dosing	X ^k										
Vital Signs (Temp, HR, BP, Respirations)	X ^l		X ^l	X ^l	X ^l	X ^l	X ^l	X ^l	X ^l	X	X
Safety Laboratory (Chemistry, Hematology)	X ^{a, m}		X	X	X	X	X	X		X	X
Physical Exam	X ^a		X	X	X	X	X	X	X	X	X
Smoking Status	X ^a								X		X
Weight	X ^a								X		
Medical History / Demographics	X ^{a, b}										
Concomitant Medication /Adverse Event Review	X		X	X	X	X	X	X	X	X	X
Overnight Fasting Lipid Panel			X	X	X	X	X	X		X	X
████████████████████	■		■	■	■	■	■	■	■	■	■
████████████████████									■		
████████████████████									■		
12-Lead Electrocardiogram (ECG)	X ^a			X				X	X		
Study Drug Dispensing	X		X	X	X	X	X	X	X ^e		
Study Drug Accountability			X	X	X	X	X	X	X	X	
Subject eDiary Daily Compliance Review			X ^h	X ^h							
Subject Symptom Recall and Compliance Review					X ⁱ	X ⁱ	X ⁱ	X ⁱ	X ⁱ	X ⁱ	
Dispense Subject eDiary	X ^h										
Return of Subject eDiary				X ^a							

Non-Site Study Procedures (Calculations for Programming/Statisticians and applicable suppliers)											
			■	■	■	■	■	■	■	■	■
									■		

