3. STATISTICAL ANALYSES

3.1. General Considerations

All individual data will be listed as measured. All statistical summaries and analyses will be performed using SAS software (SAS Institute, Cary, North Carolina, USA).

All data from scheduled and unscheduled visits will be presented in the subject listings. However, unless noted otherwise, only data from scheduled/windowed visits will be included in the summaries, statistical analysis, and calculation of derived parameters.

Summary tables and listings (e.g., post text tables and individual subject data listings are prepared according to ICH Guideline E3) include a “footer” providing explanatory notes.

Continuous data will be summarized using an 8-point descriptive summary (n, mean, standard deviation, median, interquartile range [25% quartile, 75% quartile]), minimum, and maximum) unless otherwise specified.

Categorical data will be summarized using counts and percentages. Percentages will be shown to 1 decimal place and percentages for zero counts will be omitted.

For safety assessments, summary statistics will be reported by treatment.

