3.4.3. Additional Safety Assessments

3.4.3.1. Clinical Laboratory Parameters

Laboratory data, hematology, serum chemistry and urinalysis, will be summarized in terms of observed values and changes from baseline. In addition, changes from baseline relative to normal ranges from the central lab (e.g., shifts from normal to abnormal high/low) will be summarized.

The number and percentage of subjects with clinically abnormal lab values will also be summarized by timepoint for the following criteria:

- absolute neutrophil count of $< 1.0 \times 10^9/L$

- white blood cell count of $< 2.0 \times 10^9/L$
- absolute lymphocyte count of $< 0.5 \times 10^9/L$

A listing of all abnormal lab values will be provided.

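### The SAP's low neutrophil, white cell and lymphocyte counts depend on how a repeat test is labelled, because they use only the latest record under each visit and have no any-time row

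*SAP*

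**What the plan says.** Four SAP rules act together on the laboratory threshold counts.

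- **Which records enter summaries (SAP 3.1):** "unless noted otherwise, only data from scheduled/windowed visits will be included in the summaries, statistical analysis, and calculation of derived parameters".
- **Which visit a record belongs to (SAP 3.1.3):** "The visit indicated on the CRF will be used in summaries of the data". The section is headed Visit Windows but defines no date window.
- **Which record is used when a visit has several (SAP 3.1.4):** the general default is the record closest to the nominal time, but laboratory data have a special rule: "the latest laboratory test result associated with a visit or time point will be selected for summarization". The reason given is that the protocol allows repeat tests to evaluate abnormal results.
- **What is counted (SAP 3.4.3.1):** "The number and percentage of subjects with clinically abnormal lab values will also be summarized by timepoint for the following criteria": neutrophils below 1.0, white cells below 2.0 and lymphocytes below 0.5, all × 10⁹/L. No exception to the rules above is noted, and no any-time or worst-value row is specified.

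Protocol 7.2 uses the same three cut-offs and makes repeats likely: "the investigator must recheck within 2-7 days, except for AST or ALT > 3x ULN", subject to what the investigator deems appropriate. Protocol 8.6.3 plans the same layout: "clinical laboratory abnormalities of concern will be summarized by visit, overall and by arm".

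**The concern.** The latest-record rule depends on the outcome. A repeat is most often drawn because the first value was abnormal, so the value most likely to be replaced is the one the table is meant to count. Two consequences follow.

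1. A valid low value leaves the count if its recheck carries the same visit label and has recovered. It stays if the recheck is coded unscheduled. The SAP does not say which label a repeat receives.
2. A low value found only on a record coded unscheduled is never counted.

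Changes in laboratory safety tests are part of the primary endpoint, and these are the only laboratory counts against fixed cut-offs that the SAP text specifies. Protocol 1.5 names reduced neutrophils and lymphocytes among the effects seen with a systemic JAK inhibitor and says the potential risks will be assessed in this study. Rows by timepoint also do not show how many distinct subjects ever crossed a cut-off.

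**Working it through.** The plan gives no figure here to reproduce. The check has three parts: whether a timely recheck can fall at another scheduled visit, what the rules return when applied literally, and what can be said about size.

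**Spacing of scheduled laboratory visits.** Inputs are the laboratory row ("Safety Laboratory (Chemistry, Hematology") and the visit windows in SAP Table 4. The Week 52/104/156 column is blank in that row.

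- Week 4 to Week 12, each ±5 days: 56 − 5 − 5 = 46 days minimum.
- Each later pair of weekly laboratory visits is 12 weeks apart: 84 − 5 − 5 = 74 days minimum.
- End of Study (EOS) is 4 weeks after last dose, −3 to +5 days: 28 − 3 = 25 to 28 + 5 = 33 days after last dose. Early Discontinuation is at most 5 days after last dose, so the gap between them is at least 25 − 5 = 20 days.

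A recheck at 2 to 7 days therefore carries the same visit label or is unscheduled, unless it happens to fall at an Early Discontinuation visit.

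**The rules applied literally.** Assumed neutrophil values are used with the cut-off of < 1.0. The scheduled sample is drawn on the nominal Week 12 day and the repeat five days later. Each entry is the subject's contribution to the count.

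| Scheduled value, repeat value | Label of repeat | SAP rule (latest) | Closest to nominal | Any-time |
|---|---|---|---|---|
| 0.9, 1.2 | Week 12 | 0 | 1 | 1 |
| 0.9, 1.2 | Unscheduled | 1 | 1 | 1 |
| 1.2, 0.9 | Week 12 | 1 | 0 | 1 |
| 1.2, 0.9 | Unscheduled | 0 | 0 | 1 |

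A confirmed low (for example 0.8 then 0.9) counts as 1 under either label. White cells (1.8 then 3.1) and lymphocytes (0.4 then 0.9) behave like the first two rows. Against an any-time count the SAP rule can only be too low. Against the SAP's closest-to-nominal default it can differ in either direction.

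**Size of the first consequence.** For low values at scheduled visits that call for a recheck:

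share lost = k × s × q

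Here k is the chance that a recheck is done, s the share of rechecks filed under the same visit label, and q the chance that such a recheck is no longer below the cut-off. The documents give none of these. Each can lie between 0 and 1, so the range is 0% to 100%. It is 0% if no recheck is done, if every recheck is coded unscheduled, or if every recheck stays low.

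As an illustration only, take 10 subjects low at Week 12, all rechecked (k = 1), of whom 7 recover (q = 0.7). With s = 0 the count is 10. With s = 1 it is 10 − 10 × 1 × 1 × 0.7 = 3. An any-time count is 10 in both cases. The second consequence cannot be sized either.

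**The case against.** The latest-record rule is deliberate and explained, the exclusion of unscheduled data is stated openly, and the by-visit layout follows the protocol. All of that stands, so this is not a departure from the protocol.

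SAP 3.1 and 3.1.4 also speak of windowed visits and of records within the visit window, which hints at assignment by date. The wording is not reconciled with SAP 3.1.3. Under a date reading with the ±5-day window, however, a sample on the nominal day would be displaced by a recheck on days 2 to 5 but not on days 6 to 7. The count would then depend on the recheck date instead of its label, and the weakness remains.

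Other outputs cover part of the gap. Abnormalities of concern are an adverse event of special interest (AESI) category that SAP 3.4.2.1 summarizes overall, and clinically significant values are recorded as adverse events when they meet that definition. But Protocol 7.2 ties AESI reporting of these cytopenias to two sequential low reports, so a single low value that recovers would normally not appear there. A low value at a scheduled visit that is confirmed at recheck is not lost. Listings hold every result but give no subject count.

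An any-time row may already exist in documents not seen here: "Specifications for tables, figures, and data listings are contained in a separate document". SAP 3.4 also promises summaries of notable laboratory results without defining them. Finally, the study ended early, the report is synoptic and no inferential tests are planned, which limits what is at stake.

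**Conclusion.** The concern holds as a minor point. As the SAP is written, the same results can give a count of 0 or 1 depending only on the label of the repeat, and a low value seen only at an unscheduled visit is not counted. The label dependence follows from the text and needs no assumption about rates. It does rest on taking the visit from the CRF as SAP 3.1.3 states, and on the separate table specifications not already adding an any-time row. The size is unknown and may be zero. The effect is confined to the summary counts: no data are lost, and means, changes from baseline and shift tables are not challenged here.

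**What to change.** In SAP 3.4.3.1, add for each of the three criteria one overall row counting subjects whose worst valid value after first dose meets the cut-off. Take values through the EOS visit including its window, which is 28 + 5 = 33 days after last dose. Include repeat and unscheduled results. State that this period follows the EOS laboratory sample and so runs past the 28 days used for treatment-emergent adverse events. Keep the by-timepoint rows, and leave the SAP 3.1.4 rule unchanged for means and changes from baseline.

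The cost is three table rows and one footnote, with no new data. The drawback is that subjects tested more often have more chances to show an abnormal value, and the footnote should say so. If the separate specifications already contain such rows, a sentence in SAP 3.4.3.1 saying so is enough.

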3.1.5. Actual Treatment

Data will be summarized by actual treatment group which will be determined by the treatment that was dispensed at the Day 1 visit.

3.2. Study Subjects

3.2.1. Enrollment

Not applicable for the synoptic CSR.

3.2.2. Subject Disposition and Completion Status

A summary of study disposition will be provided by study treatment on the Safety analysis set showing the following:

- Number of subjects enrolled
- Number of subjects treated
- Number of treated subjects who completed the study
- Number of treated subjects who discontinued early from the study
- Primary reasons for early study discontinuation, with frequencies
- Number of treated subjects who completed treatment
- Number of treated subjects who discontinued treatment early
- Primary reasons for early treatment discontinuation, with frequencies

A listing of subject disposition will include Safety analysis set flag [Yes/No], dates of first and last dose of study drug, primary reason for subject discontinuation of study treatment, study completion status, primary reason for study termination, and date of last contact.

3.2.3. Demographic and Baseline Characteristics

Demographic data including age, sex, race, ethnicity, weight, height, and body mass index (BMI) will be summarized overall and by treatment group. Sex, race, and ethnicity frequency distributions will be provided.

3.2.4. Protocol Deviations

The number and percentage of subjects reporting important protocol deviations will be summarized overall and by treatment group for the Safety analysis set. Important protocol deviations are defined in the protocol deviation plan.

A listing of all important protocol deviations will be provided.

3.2.5. Medical History

Medical and surgical history data will be coded using the Medical Dictionary for Regulatory Activities (MedDRA), version 24.0 or later. A listing of medical history coded to each system organ class and preferred term for each subject will be provided.

3.2.6. Prior/Concomitant Medications

Prior medications include all medications taken prior to the first dose of study drug, regardless of when they were stopped. Concomitant medications include all nonstudy medications that the subject was taking prior to the Day 1 visit that were ongoing at the visit, in addition to all medications with a start date on or after the first dose date and no later than the last dose date + 28 days. Medications with a start date after the last dose date + 28 days will be included in a listing of concomitant medications with a flag.

Recorded prior and concomitant medication names will be mapped according to [REDACTED]

3.3. Primary Analyses

The primary objective is to assess the safety and tolerability of TD-1473 administered up to 3 years in subjects with moderate to severe UC after participation in the Maintenance Study of Protocol 0157. The analyses for this objective are outlined in [Section 3.4 Safety Analyses](#). No efficacy endpoints are considered primary endpoints.

3.4. Safety Analyses

The analysis of safety data includes an overall summary of adverse event preferred terms by body/organ system, drug exposure (duration of treatment), dosing information/compliance, clinical laboratory results, vital signs and ECGs. Tables summarizing the adverse events reported by subjects who died, experienced non-fatal serious adverse events (SAE), or prematurely discontinued the study due to adverse event (AEs) will be prepared. Summaries of potentially clinically notable laboratory results and vital sign abnormalities are presented.

Inferential statistical tests will not be performed for adverse event incidence rates.

For all safety analyses, the safety analysis population will be used.

3.4.1. Extent of Exposure

Study drug exposure will be summarized using the 8-point descriptive summary presenting number of doses and duration of treatment for the study.

Duration of treatment will be displayed in days and calculated as:

$$\text{date of last dose} - \text{first dose date} + 1$$

Calculated values will be rounded to 1 significant digit in the analysis datasets.

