3.4.1.1. Treatment Compliance

Study drug compliance will be calculated as:

$$\frac{100 \times 0.5 \times (\text{number of capsules dispensed} - \text{number of capsules returned})}{(\text{date of last dose} - \text{date of first dose} + 1)}$$

Study drug compliance over the interval from first to last dose will be summarized as a continuous variable and by rounding to the nearest 0.1% and showing counts and percentages for the following disjoint categories: $\geq 120\%$; 110% to 120%; 90% to 110%; 80% to 90%; $< 80\%$.

Study drug administration information (date/time and study day) will be provided in a data listing. Study drug accountability information and study drug exposure and compliance will also be provided in data listings.

Study drug discontinuations and reasons for study drug discontinuation will be listed.

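### SAP 3.4.1, as worded, rounds each subject's treatment duration to one significant digit in the analysis datasets, which can distort the reported exposure median, quartiles and maximum

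*SAP*

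**What the plan says.** SAP section 3.4.1 (Extent of Exposure) summarises exposure with an "8-point descriptive summary presenting number of doses and duration of treatment for the study". Duration is expressed in days and equals last dose date minus first dose date plus 1. The section ends: "Calculated values will be rounded to 1 significant digit in the analysis datasets".

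Section 3.1 defines the summary: "Continuous data will be summarized using an 8-point descriptive summary", made up of n, mean, SD, median, the two quartiles, minimum and maximum. Section 3.4 names drug exposure, meaning duration of treatment, among the safety analyses, and section 3.3 sends the primary objective to section 3.4.

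Other rounding rules in the SAP are finer. Section 3.1 shows percentages to one decimal place, and section 3.4.1.1 forms the compliance categories "by rounding to the nearest 0.1" percent. Section 3.4.1.1 also plans an exposure listing: "Study drug accountability information and study drug exposure and compliance will also be provided in data listings". The disposition listing in section 3.2.2 gives "dates of first and last dose of study drug".

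**The concern.** The sentence fixes precision in the datasets, subject by subject, before any statistic is computed. It is not a display rule. One significant digit is very coarse for a variable that can run to several hundred days: a subject treated for 149 days is stored as 100 and one treated for 150 days as 200, while 250 and 349 days are both stored as 300. Order statistics taken from such data can only land on a coarse grid, or midway between two of its points.

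The study is purely descriptive and was stopped early, so actual exposure falls short of the planned three years by an amount the reader cannot guess. The exposure summary is what shows how much treatment time lies behind the adverse event percentages. A median or maximum wrong by tens of days would mislead on that point. Number of doses is in the same summary and would suffer in the same way if it were treated as a calculated value.

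**Working it through.** **Inputs.** Duration formula and rounding rule: SAP 3.4.1. Longest planned treatment, 156 weeks: SAP 1.5, so 156 × 7 = 1092 days. Early stop: SAP 1, "for all subjects the date of last dose occurred by 09SEP2021". The documents state no exposure result, so there is no figure of the plan's own to reproduce.

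**Rule.** For a duration of d days, let e be the largest power of 10 not above d. The rounded value is e × (d/e rounded half-up to an integer). Example: d = 168, e = 100, 1.68 rounds to 2, result 200.

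**Scheduled visit weeks**

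| Week | Days | Stored as | Error |
|---|---|---|---|
| 4 | 28 | 30 | +7.1% |
| 12 | 84 | 80 | −4.8% |
| 24 | 168 | 200 | +19.0% |
| 36 | 252 | 300 | +19.0% |
| 48 | 336 | 300 | −10.7% |
| 52 | 364 | 400 | +9.9% |
| 156 | 1092 | 1000 | −8.4% |

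**All whole-day durations, 1 to 1092.**
- 1064 of 1092 values change and 28 distinct values remain: 1 to 10, then 20 to 90 by tens, then 100 to 1000 by hundreds.
- The last duration not sent to a multiple of 100 is 94 days.
- The largest relative error is 50/150 = 33.3%, at 150 days; 15 days has the same relative error, 5/15.
- Rounding to one decimal place instead changes none of the 1092 values.

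**Effect on the summary.** Observed durations are not given, so one subject at each whole day is assumed, over three ranges (true → rounded):

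| Statistic | 1–180 days | 1–365 days | 1–545 days |
|---|---|---|---|
| Lower quartile | 45.75 → 50 | 92 → 90 | 137 → 100 |
| Median | 90.5 → 90 | 183 → 200 | 273 → 300 |
| Upper quartile | 135.25 → 100 | 274 → 300 | 409 → 400 |
| Maximum | 180 → 200 | 365 → 400 | 545 → 500 |
| Mean | 90.5 → 90.0 | 183.0 → 181.9 | 273.0 → 271.6 |
| Values off by more than 10% | 47% | 45% | 32% |

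The SD over 1–180 days rises from 52.1 to 58.7. The minimum stays at 1 in all three ranges, but a shortest duration of 29 or 84 days would be stored as 30 or 80.

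**The mean.** It moves by no more than 0.6% in these three ranges because errors up and down cancel. That depends on the spread. With durations evenly spread over 150–200 days, every value becomes 200 and the mean goes from 175 to 200 (+14%). Over 100–149 days, every value becomes 100 and the mean goes from 124.5 to 100 (−20%).

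**What early termination allows.** With last dose on 09SEP2021, a duration of 365 days needs a first dose on 10SEP2020, 545 days one on 14MAR2020, and 1092 days one on 14SEP2018. The documents give no first-dose dates, so the step from 1092 to 1000 is an upper bound only.

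**The case against.** The harmful reading is the less likely one. The other rounding rules in the SAP work to one decimal, and under that reading whole-day durations do not change. A literal run would also show every exposure of 95 days or more as a multiple of 100, which output review would probably catch. Section 3.1 has individual data listed as measured, and true durations can be rebuilt from the listed dose dates. The table and listing specifications are a separate document, and the Compliance and Exposure text of protocol section 8.4.3 is redacted, so a more precise rule may exist there. All the quartile shifts rest on assumed spreads, and some statistics barely move. Compliance uses the dates directly, adverse events are reported as counts and percentages of subjects, and no exposure-adjusted rate appears in the readable text.

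Most of this stands, and it limits the reach. It does not rescue the sentence. The SAP uses the decimal wording correctly in section 3.1, so a programmer may take the different term in 3.4.1 as deliberate. If one decimal place was meant, the sentence does nothing for duration, so it needs correcting on either reading. The as-measured rule does not clearly cover a derived variable such as duration. Rebuilding durations from a listing does not correct a published median or maximum. Text that cannot be seen is not held against the plan, but it cannot be relied on as the cure.

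**Conclusion.** The concern holds. Followed as written, section 3.4.1 stores durations with errors of up to 33%, and the exposure median, quartiles and maximum can be materially wrong. Under even spreads of 1–180, 1–365 and 1–545 days, quartiles move by up to about 37 days (137 to 100) and the maximum by 20 to 45 days. In the two shorter ranges the reported maximum exceeds any true duration.

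The arithmetic of the rule is certain. The size in this trial is not, because it depends on durations the documents do not give. The mean is nearly unchanged under the even spreads from day 1, but not if durations cluster within one rounding interval. A minimum of 10 days or less is unchanged.

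The damage is confined to one descriptive exposure summary and any listing drawn from the rounded variable. Compliance would be affected only if a programmer used the rounded duration as its denominator. No adverse event percentage changes. The sentence should be corrected before the exposure tables are produced, but it does not threaten the safety conclusions.

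**What to change.** Replace the last sentence of SAP section 3.4.1 with a rule that duration of treatment and number of doses are kept as whole numbers in the analysis datasets, and that only derived statistics (mean, SD, median, quartiles) are rounded, for display, for example to one decimal place. Check that the table and listing specifications and the dataset derivation carry the same rule.

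This is a one-line edit. It needs no new data and little or no programming, since the existing formula already returns whole days.
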